12.3 SUBJECT ENROLLMENT AND RANDOMIZATION

If the prospective subject meets all of the study inclusion criteria, does not meet the exclusion criteria (a checklist will be provided in the CRFs), and has signed the informed consent form, then the subject can be enrolled onto the study. Investigators or study coordinators will submit a subject randomization form to KAI to receive the subject's random dose code number. The randomization form will contain all information pertinent to the stratification variables for treatment assignment. The KAI will then return to the site, a random dose code number, which assigns the participant to a dose level.

If any subject does not actually receive any investigational agent after they have been randomized, they are considered to be a randomization failure. A randomization failure notification will be submitted to KAI.

12.4 TREATMENT PHASE

At the first clinic visit, subjects will be given instructions on how to administer the investigative agent, Bupropion or placebo, and will be given a one-week supply. This is a double-blind study in which neither the subject nor the site staff will know if the subject is receiving the investigational drug or the placebo. The subject will be given the first dose of the investigational agent in the clinic regardless of the time and will be observed for one hour to monitor for immediate adverse symptoms.

Subjects will be scheduled for treatment and assessment visits three times per week usually on a Monday, Wednesday, and Friday for 12 weeks. Two consecutive days may be scheduled around

holidays or other schedule conflicts. All subjects will be offered an opportunity for HIV testing and counseling and HIV/AIDS education (Appendix II). All subjects will be provided with CBT three times per week during the 12 weeks of treatment. Clinical evaluations are described in detail in section 12.

12.5 TREATMENT TERMINATION INTERVIEW

After the completion of dosing, (as soon as possible after the last dose of investigational agent is taken during study week 12) or at the time of premature treatment discharge, subjects will be asked to come to complete the treatment termination interview. Vital signs, physical examination, a 12-lead ECG, pregnancy test and clinical laboratory studies (blood chemistry, hematology, and urinalysis) will be performed. The ASI-Lite, HRBS, CGI-O, CGI-S, MAWQ, cognitive battery, and End of Trial form will be completed in addition to the scheduled weekly assessments. Methamphetamine and creatinine and other drug urine tests, alcohol breathalyzer, and SUR will be completed.

12.6 DROP-OUT PREVENTION

Subjects will be encouraged to come for treatment and for the evaluation sessions as described in this protocol. To minimize missed sessions, they will be reimbursed for transportation and time spent in completing study assessments. It will be emphasized to subjects during screening that even if they have a relapse they should come to all scheduled appointments. They will be discouraged from using methamphetamine, but there will be no penalty for relapsing or for missed sessions.

Subjects will be encouraged to complete study visits, assessments, and CBT sessions, even if they are unable to tolerate the investigational agents. If a subject decides to drop out of the study prior to week 12, s/he will be asked to complete all final assessments (termination) at the time of drop out. If a subject wishes to stop taking the study agent but to continue to participate in CBT sessions, s/he will continue to have all scheduled assessments according to the protocol and will complete the study at week 12. In this case, all study measures will be completed per protocol with the exception of those strictly related to the study agent.

A subject will be considered a drop out, if the subject misses six consecutive sessions during the 12 weeks of treatment. However, s/he will be asked to complete all termination assessments at the time of drop out and will be compensated for completing these assessments.

Subjects are free to discontinue the study and to refuse to participate in any of the procedures. If a subject drops out without making their intentions known, staff will attempt to contact them by telephone or written correspondence. Once the subject has been contacted and expresses their decision to discontinue from further participation in the study, the research staff will cease to try to make further contact.

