12.12 STUDY TERMINATION

12.12.1 Subject Termination

An investigator may terminate a subject if s/he deems it clinically appropriate or for any of the following reasons: (1) significant side effects from investigational agents, (2) serious or unexpected AEs, (3) failure to comply with the study protocol, (4) protocol violation, (5) positive pregnancy test, (6) serious intercurrent illness or a benzodiazepine or barbiturate medication use (see below), and (7) the subject becomes a danger to self or others. Persistent alcohol abuse will be assessed by the PI or study physician and after the third warning and consultation with NIDA, the subject may be terminated from the study.

Benzodiazepine and Barbiturate Abuse. If a subject starts using a benzodiazepine or barbiturate medication while in the study, they will likewise be given a warning by the site principal investigator or study physician to stop using these drugs, and any benzodiazepine or barbiturate urine positive beyond 3 weeks after the date the warning was given will result in discontinuation of bupropion. A three-week interval is warranted due to the long elimination time of some benzodiazepines. If a subject is prescribed a benzodiazepine or barbiturate for legitimate medical purposes, subjects will be warned that any abrupt discontinuation of either medication are known to lower seizure threshold.

Failure to comply with protocol. A subject will no longer be eligible for study participation, if s/he is absent from the clinic for more than two consecutive weeks and does not provide any data. Study participation will end if subjects miss six consecutive relapse prevention groups or consecutive urine samples. In any event, subjects will be contacted 4 weeks after treatment discharge to schedule a follow-up data interview.

Voluntary withdrawal. A subject may withdraw from the study anytime s/he wishes. In the event a subject is discontinued from receiving the investigational agents, s/he will be allowed to continue the CBT treatment with the approval of the site principal investigator.

Any subject, who discontinues prematurely, regardless of the reason, will be requested to return for a final visit to perform the necessary procedures and obtain data for the treatment discharge interview as well as 4 weeks after discharge for the follow-up interview.

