14.6 ADVERSE EVENTS REPORTING

In accordance with FDA reporting requirements, all AEs occurring during the course of the clinical trial will be collected, documented, and reported by the principal investigator or sub-investigators according to the specific instructions detailed in this section of the protocol and Appendix III. The occurrence of AEs will be assessed at each study visit and an AE CRF completed weekly.

An AE is defined as any reaction, side effect, or untoward event that occurs during the course of the clinical trial, whether or not the event is considered medication-related or clinically significant. For this study, AEs will include events reported by the subject, as well as clinically significant abnormal findings on physical examination or laboratory evaluation. A new illness, symptom, sign or clinically significant clinical laboratory abnormality or worsening of a pre-existing condition or abnormality is considered an AE. Stable chronic conditions, such as arthritis, which are present prior to clinical trial entry and do not worsen are not considered AEs. All AEs must be recorded on the AE Form. The AE Form is also used to record follow-up information for unresolved events reported on previous visits.

Each week, a study investigator must review the AE Form completed for the previous week for any events that were reported as continuing. All AEs, including clinically significant abnormal findings on laboratory evaluations, regardless of severity, will be followed by study investigators until satisfactory resolution. AEs should be reported up to 4 weeks following completion of, or termination from treatment.

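### Section 12.6 ends contact with a silent leaver who is reached and declines to continue, while sections 12.12.1 and 12.7 still call for a 4-week follow-up of that subject

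*Protocol*

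**What the plan says.** Section 12.6 (Drop-out Prevention) deals with subjects who disappear: "If a subject drops out without making their intentions known, staff will attempt to contact them by telephone or written correspondence". The next sentence gives the stopping point for that outreach: once the subject has been reached and has stated a decision to leave, "the research staff will cease to try to make further contact". The same section asks subjects who announce that they are leaving, and those counted as drop-outs after six consecutive missed sessions, to complete the termination assessments. It also lets any subject refuse any procedure.

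Section 12.12.1 (Subject Termination), in its paragraph on failure to comply with the protocol, says: "In any event, subjects will be contacted 4 weeks after treatment discharge to schedule a follow-up data interview". After the paragraph on voluntary withdrawal it adds: "Any subject, who discontinues prematurely, regardless of the reason, will be requested to return for a final visit". That sentence extends the request to the interview at 4 weeks.

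Section 12.7 (Follow-up) sets the interview for early leavers at 4 weeks after premature discharge. It covers drug use, concomitant medications and adverse events, with a telephone fallback and then the subject's named contacts. Section 14.6 gives the safety window: "AEs should be reported up to 4 weeks following completion of, or termination from treatment".

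**The concern.** Take a subject who stops attending, is reached by telephone and says they are not coming back. Section 12.6 tells the site to make no further attempt. Section 12.12.1 tells the site to make contact 4 weeks after discharge, and 12.7 lists what to collect then. Neither section exempts this subject or refers to the other. Section 12.6 treats a decision to stop taking part as though it were a refusal of any later contact, and the protocol nowhere distinguishes the two.

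A site that follows 12.6 literally skips the scheduled assessment of adverse events and drug use after study agent is stopped. The loss would fall on early leavers only, and could differ among the five sites according to which section each one follows.

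**Working it through.** **Do the sections apply to the same people?**

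| Section | Who is covered | What staff do |
|---|---|---|
| 12.6, stop-contact sentence | Left silently, then reached and stated a decision to leave | No further attempt at contact |
| 12.12.1, failure to comply | Absent for more than two consecutive weeks, or six consecutive missed groups or urine samples | Contact 4 weeks after discharge |
| 12.12.1, closing sentence on early leavers | Every premature discontinuer, whatever the reason | Request a final visit and a 4-week interview |
| 12.7 | Completers and premature discharges | 4-week interview by visit or telephone, including adverse events and drug use |

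With three visits a week, six missed sessions is 6 / 3 = 2 weeks of absence. The subjects described in the failure-to-comply paragraph of 12.12.1 are therefore largely the silent leavers of 12.6. The overlap is real: the two sections give opposite instructions for a silent leaver who is later reached.

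**How many subjects?**

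Inputs:
- Dropout rate d = 46% to 50%, from the blinded analysis of the first fifty randomized (section 15.7). As counts, 50 x 0.46 = 23 and 50 x 0.50 = 25.
- Planned size N = 150 (section 15.7).
- Share s of drop-outs who leave silently, are reached, and state a decision to discontinue. The protocol does not give s, so it is varied as an assumption.

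Expected drop-outs = N x d: 150 x 0.46 = 69 and 150 x 0.50 = 75.

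Subjects under the stop-contact rule = N x d x s:

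| Assumed s | At d = 46% | At d = 50% | Share of 150 |
|---|---|---|---|
| 10% | 6.9 | 7.5 | 4.6%-5.0% |
| 25% | 17.25 | 18.75 | 11.5%-12.5% |
| 50% | 34.5 | 37.5 | 23%-25% |
| 75% | 51.75 | 56.25 | 34.5%-37.5% |
| 100% | 69 | 75 | 46%-50% |

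The figure of 69 to 75 is reached only if every drop-out left silently, was reached, and said they would not continue.

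**Which data?** The primary outcome (15.4.1) is built from urine samples taken during the 12 treatment weeks, and the methamphetamine-use secondaries in 15.4.2 are listed for the same period. None of these is collected at the 4-week contact. Adverse events are a listed safety outcome (15.4.2), and their window runs 4 weeks past termination (14.6). The exposed data are those adverse events, the 4-week drug-use report and, where the rule is triggered before a final visit has been arranged, possibly the termination assessments.

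**The case against.** The best defence is that the stop-contact sentence, read in place, only closes the outreach described just before it. Section 12.6 handles announced leavers separately and asks them for termination assessments. The final visit and the 4-week interview only have to be requested, and both requests could be made in the call in which the subject states the decision. Section 12.12.1's unconditional sentence sits in the paragraph on non-compliance and is not repeated under voluntary withdrawal. Section 14.7 separately requires medical follow-up after withdrawal for a serious adverse event, and 14.6 has all adverse events followed to resolution. Since subjects may refuse any procedure, some loss would occur under any wording.

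Much of this stands, and it limits the point to silent leavers who are later reached. It does not remove the conflict. A contact 4 weeks after discharge is ordinarily a later contact, so 12.6 rules it out even if requests were made in the earlier call. Nothing in 12.6 tells staff to make those requests before they stop. The non-compliance paragraph describes largely this same group. Following known events to resolution does not detect new ones, and it is itself harder without contact.

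A reader might infer four stronger things that the protocol does not support:
- That contact ends for everyone who says they are leaving. The context of 12.6 is narrower.
- That data are lost in about half the trial. That is the ceiling, because the share s is not given.
- That 14.6 orders a contact. It sets a reporting window.
- That the efficacy result is compromised. The primary outcome does not use this contact.

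**Conclusion.** The point holds in a narrow form. For a silent leaver who is reached and states a decision to discontinue, section 12.6 cannot be reconciled as written with the 4-week contact in 12.12.1 and 12.7, because leaving treatment and refusing follow-up are not separated. The number affected is unknown: at most 69 to 75 of 150, and 17 to 19 on the illustrative assumption that s is 25%. Both ranges also assume that dropout in the first fifty carries over to all 150. At stake are post-treatment safety and drug-use data, and possibly the termination visit, in early leavers. With dropout near half, this is worth correcting, though it does not threaten the primary analysis.

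**What to change.** Reconcile 12.6 with 12.12.1 and 12.7 by adding a clause to 12.6. It should say that, after a subject states a decision to discontinue, staff end their efforts to bring the subject back to treatment visits. The termination request and the single 4-week contact, by visit or by telephone as 12.7 already allows, are still made unless the subject refuses that contact itself.

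The means exist: the locator form (13.6.1) asks for consent to follow-up and collects contact details, and the follow-up questionnaire (13.6.31) records whether contact was made. Locator-form consent would not override a later refusal, and the clause respects that.

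The cost is one clause and one more contact attempt per affected early leaver: about 17 to 19 attempts at the illustrative 25% share, and no more than 69 to 75 at the ceiling. Data from subjects who refuse the contact itself will still be missing.

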12.7 FOLLOW-UP (WEEK 16)

Subjects will be asked to return to the clinic 30-days after completion of treatment. During the follow-up interview (week 16 or 4 weeks after the premature treatment discharge date), the

subject will be asked to provide a urine specimen for methamphetamine/creatinine and urine drug screen and provide a self-report for use of methamphetamine, cocaine, opiates, alcohol, cigarette smoking, and marijuana. The subject will also be asked to provide any current treatments for drug or alcohol abuse. Concomitant medications and adverse events will be assessed, and the subject will complete the follow-up form. If it is not possible to arrange for the subject to return to the clinic, then they should be telephoned and asked to provide a current self-reported methamphetamine and other drug use, current treatment for drug or alcohol abuse. Concomitant medications and adverse events will be assessed over the telephone as well as the follow-up form. If a subject cannot be contacted directly, attempts will be made to reach the individual(s) previously identified by the subject as a contact source.

12.8 MAINTAINING AND BREAKING STUDY BLIND

The decision to break the study blind for an individual subject lies with the site principal investigator and project principal investigator or with the NIDA medical monitor, but should be resorted to only in cases of life-threatening emergency when knowledge of the treatment arm investigational drug will influence clinical management.

12.9 SAFETY PROCEDURES

Participants judged by the site principal investigator and/or study physician at any point to be a danger to self or others or who are judged to be in grave danger due to continued study agent use and/or to extreme psychiatric problems will be discontinued from the study and connected with an appropriate treatment agency. All staff will receive training in identifying suicide/homicide risks and/or signs of dangerous intoxication to any substance and the steps needed to appropriately respond to these signs.

12.10 SUBJECT REIMBURSEMENT

Subjects will be reimbursed for travel expenses, for providing data, and for time contributed to this research study. Subjects will receive \$10 in retail scrip or vouchers or other acceptable form of reimbursement for each clinic visit in which a urine specimen is provided during screening and the 12 weeks of treatment as reimbursement for their time and travel expense. Travel expenses (bus and cab fares) may be paid with an acceptable form of reimbursement. Subjects will be paid \$25 in retail scrip or vouchers or other acceptable form of reimbursement for the study termination interview and the week 16 follow-up assessment. Payment will be made upon completion of the specified requisite assessments for a maximum payment of \$530 in retail scrip or vouchers. They will be compensated regardless of whether they continue to receive the investigational agent.

12.11 SUBJECT CONFIDENTIALITY

To maintain subject confidentiality, all laboratory specimens, CRFs, reports, and other records will be identified by a coded number and name code only. Research and clinical records will be stored separately in a secure location and only the investigative staff will have access to the records. Subject information will not be released without the written permission, except as

necessary for monitoring by the FDA, NIDA or other regulatory agencies. Upon approval of the study by the site IRB, an application will be filed with NIDA for a certificate of confidentiality.

12.12 STUDY TERMINATION

12.12.1 Subject Termination

An investigator may terminate a subject if s/he deems it clinically appropriate or for any of the following reasons: (1) significant side effects from investigational agents, (2) serious or unexpected AEs, (3) failure to comply with the study protocol, (4) protocol violation, (5) positive pregnancy test, (6) serious intercurrent illness or a benzodiazepine or barbiturate medication use (see below), and (7) the subject becomes a danger to self or others. Persistent alcohol abuse will be assessed by the PI or study physician and after the third warning and consultation with NIDA, the subject may be terminated from the study.

Benzodiazepine and Barbiturate Abuse. If a subject starts using a benzodiazepine or barbiturate medication while in the study, they will likewise be given a warning by the site principal investigator or study physician to stop using these drugs, and any benzodiazepine or barbiturate urine positive beyond 3 weeks after the date the warning was given will result in discontinuation of bupropion. A three-week interval is warranted due to the long elimination time of some benzodiazepines. If a subject is prescribed a benzodiazepine or barbiturate for legitimate medical purposes, subjects will be warned that any abrupt discontinuation of either medication are known to lower seizure threshold.

Failure to comply with protocol. A subject will no longer be eligible for study participation, if s/he is absent from the clinic for more than two consecutive weeks and does not provide any data. Study participation will end if subjects miss six consecutive relapse prevention groups or consecutive urine samples. In any event, subjects will be contacted 4 weeks after treatment discharge to schedule a follow-up data interview.

Voluntary withdrawal. A subject may withdraw from the study anytime s/he wishes. In the event a subject is discontinued from receiving the investigational agents, s/he will be allowed to continue the CBT treatment with the approval of the site principal investigator.

Any subject, who discontinues prematurely, regardless of the reason, will be requested to return for a final visit to perform the necessary procedures and obtain data for the treatment discharge interview as well as 4 weeks after discharge for the follow-up interview.

If at any time during the course of the study, psychiatric symptoms are so severe as to require medication outside of the protocol and/or hospitalization, the participant should be terminated from the study protocol and treated clinically. Study participants withdrawn from the protocol secondary to a medical or psychiatric concern will be referred for appropriate treatment. Subjects will be asked to sign a general consent for the release of information to the referred health care. Study staff may request transportation for emergency treatment of a subject if medically appropriate (e.g., for acutely psychotic or suicidal subjects).

All study participants will be encouraged to carry a wallet card that identifies them as a participant in a clinical research study. The card will provide the name and phone number of the site principal investigator (physician) at the site who can be contacted in the event of an emergency. If possible, the card should also instruct the non-study physician rendering emergency care to provide information to the study physician with regards to that care.

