10.5 SAFETY CONSIDERATIONS

One of the potentially most serious adverse effects of bupropion is reduction in the seizure threshold (Johnston *et al.*, 1991, Settle, 1998, Storow, 1994). Bupropion is contraindicated in

patients with a seizure disorder or a predisposing factor for seizures (e.g., cranial trauma history, current seizure disorder, concomitant use of drugs that lower seizure threshold). However, the relative risk of seizures with various antidepressants, including bupropion, has not been clearly defined and the incidence of seizures at doses of 400 mg daily as extended release tablets increases to 0.4%.

The incidence of seizures with bupropion depends on dose. Minimizing the risk of seizures includes restriction of total dosage to 400 mg daily as sustained-release. Administration of the daily dose in divided doses up to 150 mg twice daily, at least 8 hours apart, should minimize the risk of seizures.

Subjects will be cautioned not to take concomitant medications, whether prescription or over the counter (OTC) medications, or herbal supplements without consulting the site principal investigator or study physician.

These include:

- All antidepressants
- Neuroleptics
- Systemic corticosteroids
- Xanthines (i.e., theophilline, theophilline sodium glycinate and aminophylline)
- Medications that interfere with methamphetamine detection in urine samples (e.g. ephedrine and pseudoephedrine)

Subjects will be asked to inform a study physician, if they decide to use any smoking cessation products such as nicotine gum, nicotine patch, nicotine nasal spray or nicotine inhaler while on study. If any agents are used, blood pressure should be monitored closely as bupropion may increase blood pressure when used with these smoking cessation agents.

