12.13 CONCOMITANT MEDICATIONS

Any medications (including prescription, over-the-counter, herbal supplements and health store products) to be taken during the study must be approved by the site principal investigator. Medications that should not be taken at any time during the study are presented in section 10.5.

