Following randomization, during the treatment phase of the study and at each of the follow-up visits, urine will be collected 3 times per week (generally Monday, Wednesday, and Friday, barring holidays and schedule conflicts) and NWT will screen the first sample collected each week for cocaine, methamphetamine/amphetamines, tetrahydrocannabinol, barbiturates, opiates, and benzodiazepines. NWT will screen all samples for amphetamines/methamphetamine and quantitative creatinine, and NWT will quantitate amphetamines and methamphetamine for all samples, which screen positive by NWT for methamphetamine/amphetamines.

All specimens collected during this time frame and screened positive by NWT for methamphetamine/amphetamines will be subjected to methamphetamine quantitative analysis performed at NWT for the determination of "new use." The back-up sample retained at the site will be stored frozen until the NIDA data-coordinating center has notified the site that it can be disposed.

Urine Toxicology Screen Using an Onsite Testing Device. During the screening and baseline period, urine will be collected 3 times per week (generally Monday, Wednesday, and Friday, barring holidays and schedule conflicts). After the backup aliquot and central laboratory testing aliquot has been taken, these samples will be analyzed using an on-site testing device (tetrahydrocannabinol, methamphetamine, cocaine, amphetamines, barbiturates, opiates, benzodiazepines, tricyclics, and phencyclidine). Samples positive for amphetamine (the onsite testing device has a cutoff of greater than or equal to 1000 ng/mL) will be considered as positive for methamphetamine for inclusion criteria purposes.

During treatment and after the backup aliquot and central laboratory testing aliquot has been taken, the first urine sample collected each week will be analyzed using an on-site testing device.

A frozen aliquot of every sample will be stored at the site. At treatment termination and followup, samples will be sent to a central lab for analysis, be subjected to onsite testing, and an aliquot will be frozen on site as back up. Results of on-site testing will be provided to the clinical staff as well as the investigative staff for the safety of the subjects.

Medical Urinalysis. Urine will be collected and analyzed for specific gravity, pH, blood, protein, glucose, ketones, leukocytes, and nitrites. The analysis will be conducted at a central clinical laboratory.

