13.6.18 Adverse Events (AEs)

AEs will be assessed and recorded at each visit by an investigative staff nurse or physician or qualified research assistant. If an AE that requires medical attention is reported to a nurse or research assistant, it will be reported to a study physician immediately. A study physician will meet with the subject once a week to review the AEs recorded by the nurse and to assess for any additional AEs. The investigator or study physician will assess subjects for any medical or psychiatric side effects. Both the staff nurse, research assistant or the physician will assess AEs by asking the participant "How have you been feeling since I saw you last". The type of AE, severity of the AE, and the relationship to the study treatments will be recorded on an AE CRF according to the procedures described in section 13.6.

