13.6.20 Concomitant Medications

All medications taken by the subject after consent during screening, while on study, and at the final follow-up assessment will be recorded on a Concomitant Medications form. The reported medications will be reviewed by the site investigator/study physician for possible drug interactions. Medications that should not be taken at any time during the study are the following: all antidepressants, neuroleptics, systemic corticosteroids, and xanthines, i.e., theophilline, theophilline sodium glycinate and aminophylline.

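### Protocol section 12.12.1 tells anyone who starts a benzodiazepine or barbiturate to stop, but requires the abrupt-withdrawal seizure warning only for legitimate prescriptions

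*Protocol*

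**What the plan says.** The paragraph on benzodiazepine and barbiturate abuse in Protocol section 12.12.1 contains three instructions.

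- **Stop warning.** When a subject starts one of these drugs during the study, "they will likewise be given a warning by the site principal investigator or study physician to stop using these drugs". This sentence does not separate prescribed from non-prescribed use, and it mentions neither tapering nor seizures.
- **Time limit.** After that, "any benzodiazepine or barbiturate urine positive beyond 3 weeks after the date the warning was given will result in discontinuation of bupropion". The paragraph explains the three weeks by the slow elimination of some benzodiazepines.
- **Seizure warning.** "If a subject is prescribed a benzodiazepine or barbiturate for legitimate medical purposes, subjects will be warned that any abrupt discontinuation" of either drug is known to lower the seizure threshold. The sentence opens with a condition, and that condition is a legitimate prescription.

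Section 10.5 supplies the background: "One of the potentially most serious adverse effects of bupropion is reduction in the seizure threshold". It also says that bupropion is contraindicated in patients with a seizure disorder or a predisposing factor for seizures, and gives examples.

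**The concern.** The paragraph recognises a hazard, abrupt withdrawal of a sedative, and prescribes advice about it. It then limits that advice to subjects with a legitimate prescription. The pharmacology it relies on does not depend on the source of the drug. The group left out is the one that a paragraph about abuse mainly concerns, and it is plainly within the instruction to stop.

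What is at stake is a preventable seizure in someone who follows the instruction. Such a subject may at the same time be taking a study drug whose own main safety concern is the seizure threshold. Nothing in the efficacy analysis is touched.

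**Working it through.** No arithmetic applies. The documents give no rate of on-study benzodiazepine or barbiturate use and no withdrawal-seizure risk. The check sets the relevant provisions side by side.

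**1. Who is told to stop, and who must get the seizure warning (section 12.12.1).**

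| Subject who starts the drug on study | Told to stop? | Seizure warning required? |
|---|---|---|
| Non-prescribed use | Yes | No |
| Legitimately prescribed | Unclear | Yes |

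The stop sentence covers anyone who starts one of these drugs, so it can be read to include prescribed users. The last sentence can also be read as an exception for them. On the first reading, one of the two kinds of user told to stop lacks the required advice. On the second, the only users told to stop are the ones without it. The gap exists either way.

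**2. Does the 3-week rule cover it?** No. It acts on a subject whose urine is still positive more than three weeks after the warning. A subject who stops at once and turns negative does not trigger it and may continue study agent. The withdrawal hazard belongs to the subject who stops abruptly, and the rule addresses the one who does not stop.

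**3. Does another provision require the advice?** Each candidate was read for that purpose.

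- Section 9.2, exclusions 1 to 3: these remove sedative dependence needing detoxification, seizure history and current use of threshold-lowering drugs. They apply at entry and not to use begun later.
- Section 10.5: subjects are cautioned not to take other medications without consulting the site principal investigator or study physician. It says nothing about stopping sedatives.
- Section 12.9: a subject judged to be in grave danger from continued study agent is discontinued, and staff are trained to recognise dangerous intoxication. Neither provision prescribes withdrawal advice.
- Section 12.12.1 itself: benzodiazepine or barbiturate use is among the reasons for which an investigator may terminate a subject. That is discretionary.
- Section 12.13: medications "to be taken during the study must be approved by the site principal investigator". This governs permission to take a drug.
- Section 13.6.14: "Results of on-site testing will be provided to the clinical staff as well as the investigative staff for the safety of the subjects". The on-site panel includes benzodiazepines and barbiturates, so use is likely to be detected, but no advice follows from the result.
- Section 13.6.18: "A study physician will meet with the subject once a week to review the AEs". This is an opportunity to advise, without a requirement.
- Section 13.6.20: "The reported medications will be reviewed by the site investigator/study physician for possible drug interactions". The review is of reported medications, and use found only by urine screen is not expressly covered.

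The conditional sentence in section 12.12.1 is the only one in the available text about abruptly stopping these drugs.

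**The case against.** The best case for the plan has four parts.

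**The distinction may be deliberate.** Non-prescribed users in this paragraph have only just started, sedative dependence needing detoxification was excluded at entry, and weekly screening should find new use early. A withdrawal warning aimed at people on a prescribed course is then a defensible choice. This lowers the expected number at risk, and the documents give no evidence of a high hazard in recent users. But the paragraph gives no such reason, and weekly screening does not show how much a subject has been taking.

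**A physician delivers the message.** The site principal investigator or study physician gives the stop warning, and adverse events are assessed at every visit. Either person may well mention seizures. This stands as mitigation, but the advice is still left to chance for one group and required for the other.

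**Other documents may carry it.** Consent pages are not in the copy reviewed, and section 16 refers to an operations manual. Either could contain wider advice. This also stands, so the finding is confined to the text at hand. A wider warning elsewhere would still leave this sentence too narrow.

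**It is a drafting matter.** Largely so, and the severity is set accordingly.

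A reader might also infer more than the text supports:

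- *That the protocol orders abrupt stopping.* It says to stop and is silent on how.
- *That the 3-week rule is the only mandatory action on study agent.* Section 12.9 also requires discontinuation once grave danger is judged.
- *That half of those told to stop go unwarned.* The prescribed group may not be told to stop at all, and two categories of unknown size give no proportion.
- *That sedative withdrawal is a listed contraindication.* Section 10.5 does not name it, although its list is given as examples.

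**Conclusion.** The point holds as a minor subject-safety correction. Section 12.12.1 states a hazard of stopping these drugs and then requires the matching advice for a narrower group than the hazard covers. Non-prescribed users are told to stop with no seizure advice required in the visible text, and those randomized to bupropion are also taking a drug that lowers the seizure threshold.

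The size cannot be calculated. The number affected is unknown and probably small, given the entry exclusion and the general safeguards. The conclusion rests on the wording of section 12.12.1, on the description of bupropion in section 10.5, and on the absence of any other provision requiring the advice in the text available. It does not depend on which way the prescribed-user sentence is read. There is no consequence for the primary endpoint, the type I error rate or power.

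**What to change.** Remove the prescription condition from the last sentence of the paragraph. Every subject told to stop a benzodiazepine or barbiturate, prescribed or not, should be warned at that same contact that abrupt discontinuation can lower the seizure threshold. Keep the warning for prescribed users whether or not they are told to stop. Leave the 3-week rule as it is.

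The cost is about one sentence of protocol text. No visit, test or contact is added, because the stop warning already has to be given by the site principal investigator or study physician.

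Having that person also consider withdrawal risk at the contact would be sensible but is optional. A recorded decision on whether study agent continues would go beyond the wording gap shown here and might lead a few subjects to stop study agent earlier, so it is not part of this recommendation.
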